## 7.2. Secondary Efficacy Analysis – Time to First HES Flare

### 7.2.1. Endpoint / Variables

The time to first HES flare will be calculated from the date of first dose of study treatment and the onset date of the first HES flare as defined in Section 16.6.4.

### 7.2.2. Summary Measure

The difference between mepolizumab and placebo in the time to first HES flare.

### 7.2.3. Strategy for Intercurrent (Post-Randomization) Events

The treatment effect to be estimated (estimand) will be the ‘treatment policy’ effect of initial randomised treatment. A treatment policy strategy will be used for the intercurrent events of a) discontinuation of study medication and b) receipt of alternative HES medications. If a subject withdraws prematurely from the study prior to experiencing a HES flare, the event time will be censored at the time point at which the subject withdrew from the study. Sensitivity analyses will be performed to examine the potential impact of the missing data.

### 7.2.4. Statistical Analyses / Methods

Details of the planned displays are provided in [Appendix 10: List of Data Displays](#) and will be based on GSK data standards and statistical principles.

Time to first HES flare will be graphically represented using a Kaplan-Meier plot of cumulative incidence rates over time for each treatment group.

#### 7.2.4.1. Statistical Methodology Specification

Endpoint

 
Time to first HES flare.
 

Model Specification

 
Log-rank test stratified by baseline OCS dose (<math>0 \leq 20</math>mg/day and <math>>20</math>mg/day prednisone or equivalent) and region.
 
Supplemented by a Cox proportional hazards regression model allowing for covariates of baseline OCS dose (continuous scale) and region.
 

Model Checking & Diagnostics

 
To examine the fit of the Cox proportional hazards model, martingale and deviance residuals will be calculated and plotted.
 

Model Results Presentation

 
In each treatment group             
 
Number of subject analysed.
 
Number of subjects with HES flare.
 
 
 

- Number of subjects censored at study withdrawal.
- Number of subjects censored at study completion.
- Stratified Log-Rank test p-value for association between treatment and time to first HES flare.
- Hazard ratio and 95% CI from Cox proportional hazards model.
- Wald chi-square p-value from Cox proportional hazards model.

**Subgroup Analyses**

- No subgroup analyses will be performed on this endpoint.

**Sensitivity and Supportive Analyses**

- Sensitivity analyses to assess the impact of missing data will be performed using the ITT population as follows:
  - Subjects withdrawing from the study prematurely prior to reporting a HES flare will be included with a HES flare on the date of study withdrawal.
  - Subjects withdrawing from the study prematurely prior to reporting a HES flare, with primary reason for treatment withdrawal reported as Adverse Event or Lack of Efficacy will be included as a HES flare on the date of study withdrawal. For subjects withdrawing from the study prematurely prior to reporting a HES flare, with any other reason for discontinuation of study treatment, the event time will be censored at the date of study withdrawal.

### **7.3. Secondary Efficacy Analysis – Proportion of Subject Who Experience a HES Flare During Week 20 Through Week 32**

#### **7.3.1. Endpoint / Variables**

HES flare during Week 20 through Week 32 will be defined as a HES flare starting or ongoing on or after the date of the Week 20 visit up to and including the date of the Week 32 visit.

#### **7.3.2. Summary Measure**

The difference between mepolizumab and placebo in the proportion of subjects with HES flare during Week 20 through Week 32.

#### **7.3.3. Strategy for Intercurrent (Post-Randomization) Events**

The treatment effect to be estimated (estimand) will be the ‘treatment policy’ effect of initial randomised treatment. A treatment policy strategy will be used for the intercurrent events of a) discontinuation of study medication and b) receipt of alternative HES medications. Subjects who withdraw prematurely from the study prior to Week 32 (Visit 11) and therefore have missing data on HES flares during Week 20 through Week 32 will be included in the analysis as treatment failures i.e., that they experience a flare during Week 20 through Week 32. Sensitivity analyses will be performed to examine the potential impact of the missing data.

#### **7.3.4. Statistical Analyses / Methods**

Details of the planned displays are provided in [Appendix 10](#): List of Data Displays and will be based on GSK data standards and statistical principles.

A summary of HES flares during Week 20 through Week 32 will be produced as for the primary endpoint (see Section [7.1.4](#)).

**7.3.4.1. Statistical Methodology Specification**

Endpoint

 
Proportion of subjects who experience a HES flare during Week 20 through Week 32.
 

Model Specification

 
Cochran-Mantel-Haenszel test stratified by baseline OCS dose (0-≤20mg/day and >20mg/day prednisone or equivalent) and region.
 
Supplemented by a logistic regression analysis adjusting for covariates of baseline OCS dose (continuous scale), region, and treatment.
 

Model Checking & Diagnostics

 
To examine the fit of the logistic regression model, deviance residuals will be calculated and plotted.
 

Model Results Presentation

 
Number of subjects analysed in each treatment group.
 
Number of subjects with ≥1 HES flare during Week 20 through Week 32 in each treatment group.
 
Test statistic and p-value for association between treatment and flare from Cochran-Mantel-Haenszel test.
 
Odds ratio and 95% CI from logistic regression model.
 
p-value from logistic regression model.
 

Subgroup Analyses

 
No subgroup analyses will be performed on this endpoint.
 

Sensitivity and Supportive Statistical Analyses

 
Sensitivity analyses to assess the impact of missing data will be performed using the ITT population as follows: 
 
Subjects withdrawing from the study prematurely prior to reporting a HES flare during Week 20 through Week 32, with the primary reason for treatment withdrawal reported as AE or Lack of Efficacy, will be classed as experiencing a HES flare during Week 20 through Week 32. Subjects withdrawing from the study prematurely with any other reason for treatment withdrawal will be included as having a flare if one is recorded during Week 20 through Week 32 prior to study withdrawal, and as not having a flare if no flare during Week 20 through Week 32 is recorded prior to study withdrawal.
 
Subjects withdrawing from the study prematurely will be included as having a flare if one is recorded during Week 20 through Week 32 prior to study withdrawal, and as not having a flare if no flare during Week 20 through Week 32 is recorded prior to study withdrawal.
 
 
 

## **7.4. Secondary Efficacy Analysis – Rate of HES Flares**

### **7.4.1. Endpoint / Variables**

The rate of HES flares will be calculated for each subject as the number of observed HES flares divided by the time (expressed in years) between the first dose of study treatment and either the Week 32 visit date if available, or otherwise the study withdrawal date (see Section [16.6.4](#)).

The number of observed HES flares will be calculated for each subject as the number of unique starting dates for HES flares. To be considered as a separate episode of HES flare, the onset date of a HES flare must be at least 14 days apart from the resolution date of the preceding HES flare.

For flares meeting endpoint definition b) described in Section [7.1.1](#), each subsequent course of blinded active OCS beyond 14 days from the resolution date of the preceding flare will be considered as an additional flare (e.g., 3 courses of blinded active OCS are considered as 2 flares, 4 courses of blinded active OCS are considered as 3 flares, etc.).

See Section [16.6.4](#) for details of the definition of the onset and resolution date of HES flares and full details of the derivation of the rate of HES flares.

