7.3. Efficacy

7.3.1. HES flare

An HES flare is defined as *either*

- a) An HES-related clinical manifestation based on a physician-documented change in clinical signs or symptoms resulting in the need for either of the following:
 - An increase in the maintenance OCS dose by at least 10mg/day for 5 days

- An increase in or addition of any cytotoxic and/or immunosuppressive HES therapy

or

- b) Receipt of two or more courses of blinded active OCS during the treatment period.

The start date for an HES flare meeting flare endpoint definition ‘a)’ will be defined as the date of therapy escalation confirmed by the investigator attributable to an HES-related clinical manifestation. The start date for an HES flare meeting flare endpoint definition ‘b)’ will be defined as the date of the blood draw at which the second course of blinded active OCS was triggered via scheduled blood sampling for eosinophil monitoring.

When a subject experiences an HES flare as defined in ‘a)’ above, the investigator will monitor the change in disease control per routine medical care (e.g., follow-up call) and record the resolution of the flare including the end date. Investigators are encouraged, as medically appropriate, to return the subject’s treatment regimen to the baseline (randomization) after the flare has resolved.

An increase in blood eosinophils only (without any other clinical manifestations) during the study may trigger an alert which will result in administration of additional blinded OCS (active treatment) [Section 6.4]. When a subject receives the second course of blinded active OCS during the 32-week treatment period, the subject will be considered to be experiencing a flare. Subsequently, the date of the first blood draw at which blood eosinophil count is below the threshold to trigger blinded active OCS will be the resolution date. Each subsequent course of blinded active OCS beyond 14 days from the resolution date of the preceding flare will be considered as an additional flare (e.g., 3 courses of blinded active OCS are considered as 2 flares, 4 courses of blinded active OCS are considered as 3 flares, etc.).

For subjects who reduce the dose of HES therapy after randomization for safety reasons (Section 4.1), the increase in HES therapy used to define an HES flare will be the change from the dose at randomization.

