The rate of HES flares will be calculated for each subject as the number of observed HES flares divided by the time (expressed in years) between randomisation and either the week 32 visit date if available, or otherwise the study withdrawal date. The number of observed HES flares will be calculated for each subject as the number of unique starting dates for HES flares. To be considered as a separate episode of HES flare, the start date of an HES flare must be at least 14 days apart from the resolution date of the preceding HES flare. See Section 7.3.1 for detailed definitions of flare start and resolution dates. For subjects withdrawing prematurely from the study during the 32 week treatment period, all data up to the time of study withdrawal will be used to calculate the rate of HES flares. Sensitivity analyses to assess the impact of missing data will be performed with full details provided in the RAP.

The rate of HES flares will be compared between treatment groups using a stratified Wilcoxon Rank Sum test, stratified by baseline OCS dose and region. This analysis will be supplemented by an analysis using a negative binomial generalised linear model with a log link-function. The model will include terms for treatment group, region, baseline OCS dose and observed time (as an offset variable). The estimated mean rates per year, treatment ratio and confidence limits will be presented.

Change from baseline in fatigue severity based on BFI item 3 (worst level of fatigue during past 24 hours) at Week 32

The change from baseline in fatigue severity (worst level of fatigue during past 24 hours) at week 32 will be calculated using the mean of the 7 daily assessments of BFI item 3 up to and including the date of the week 32 visit as the week 32 assessment, and the mean of the 7 daily assessments of BFI item 3 up to and including the date of randomisation as the baseline assessment. Subjects withdrawing prematurely from the study during the 32 week treatment period will be assumed to have the largest (i.e., worst) value observed for any subject for the change from baseline BFI item 3 at week 32. Sensitivity analyses to assess the impact of missing data will be performed with full details provided in the RAP.

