
 
• The onset and resolution dates of HES flares meeting endpoint definition a) will be recorded on the 'Flare details' form in the eCRF.
 
• The start date of HES flares meeting endpoint definition b) is defined as the date of the blood draw at which the second course of blinded active OCS was triggered via schedule blood sampling for eosinophil monitoring. The resolution date for a flare meeting endpoint definition b) is the date of the first blood draw at which blood eosinophil count is below the threshold to trigger blinded active OCS (see protocol Section 6.4 for full details of blood eosinophil monitoring).
 

HES flare during Week 20 through Week 32

 
• Defined as a HES flare starting or ongoing on or after the date of the Week 20 visit (Visit 8) up to and including the date of the Week 32 visit (Visit 11).
 

Time to First HES Flare

 
• Calculated for each subject as (Onset date of first HES flare – Date of first dose of study treatment) + 1
 

HES Flare
Rate of HES Flares

 
For subjects completing the study, the rate of HES flares will be calculated as <math display="block">\frac{365.25 \times \text{Number of observed HES flares}}{\text{Date of Week 32 (Visit 11)} - \text{Date of first dose of mepolizumab} + 1}</math> 
 
For subjects withdrawing prematurely from the study, the rate of HES flares will be calculated as <math display="block">\frac{365.25 \times \text{Number of observed HES flares}}{\text{Date of study withdrawal} - \text{Date of first dose of mepolizumab} + 1}</math> 
 
 
The number of HES flares is the number of unique starting dates for HES flares. To be considered as a separate episode of HES flare, the start date of a HES flare must be at least 14 days apart from the resolution date of the preceding HES flare.
 
 
For flares meeting endpoint definition b), each subsequent course of blinded active OCS beyond 14 days from the resolution date of the preceding flare will be considered as an additional flare (e.g., 3 courses of blinded active OCS are considered as 2 flares, 4 courses of blinded active OCS are considered as 3 flares, etc.).
 

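### Do the two 14-day wordings for repeat eosinophil-triggered flares, and the missing onset date for a third course, need fixing before the flare rate is derived?

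*SAP*

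**What the plan says.** A definition (b) flare is one reached through two or more courses of blinded active OCS. Three statements govern how repeats are counted.

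- General rule for separate episodes, SAP 7.4.1: "the onset date of a HES flare must be at least 14 days apart from the resolution date of the preceding HES flare". SAP 16.6.4 and protocol 9.4.1 repeat it. A gap of exactly 14 days qualifies.
- Rule for repeat definition (b) flares, SAP 7.4.1: an additional flare is "each subsequent course of blinded active OCS beyond 14 days from the resolution date of the preceding flare". SAP 16.6.4 and protocol 7.3.1 repeat it. Read strictly, a gap of exactly 14 days does not qualify. The same sentence carries an illustration in brackets: "3 courses of blinded active OCS are considered as 2 flares, 4 courses of blinded active OCS are considered as 3 flares".
- Counting unit, SAP 7.4.1: "the number of unique starting dates for HES flares". For definition (b), SAP 16.6.4 gives the start as "the date of the blood draw at which the second course of blinded active OCS was triggered", and the resolution as the first draw below the trigger threshold. It states no start for a third or later course.

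**The concern.** The two bounds differ only at 14 days, and the schedule points at 14 days. Visits are 4-weekly. Under protocol 6.4, a subject who starts blinded OCS is rechecked about 2 weeks after the visit, and a count below threshold ends the course. That draw is the resolution date, so the next scheduled visit is nominally 28 − 14 = 14 days later. If the count is again above threshold, one sentence gives a new flare and the other does not.

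The missing start date adds to the doubt. If only the second course has an onset, counting start dates literally yields one flare for any number of courses, which contradicts the plan's own illustration.

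Two secondary endpoints could be touched: the flare rate (fourth in the hierarchy) and the Week 20 to 32 proportion (third). For the latter, take a second course triggered at Week 16 (day 112), resolution at Week 18 (day 126) and a third course at Week 20 (day 140). The gap is 140 − 126 = 14 days, and a subject with no other flare in the window counts only if the third course is a new flare. The list identifying active OCS containers joins the data together with the treatment codes (SAP 16.6.4), so a rule left open could be settled with treatment codes available.

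**Working it through.** **Inputs.** Visit spacing 28 days; recheck about 14 days after the visit (protocol 6.4); visit window ±1 week (protocol 7.1). Rate = 365.25 × flares / (Week 32 date − first dose date + 1) (SAP 16.6.4). With Week 32 at first dose + 224 days (SAP 16.6.1), the denominator is 225 days.

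**1. The plan's own illustration.** Courses triggered at Weeks 4, 8, 16 and 24 (days 28, 56, 112, 168), each with a below-threshold recheck 14 days later. The first flare starts on day 56 and resolves on day 70. Gaps: 112 − 70 = 42 and 168 − 126 = 42. Both bounds give 2 flares after three courses and 3 after four, as the plan states.

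**2. The tie.** Courses at Weeks 4, 8 and 12: resolution on day 70, third trigger on day 84.

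| Gap from resolution to third trigger | Inclusive bound | Strict bound |
|---|---|---|
| 13 days | 1 flare | 1 flare |
| 14 days | 2 flares, 365.25 × 2 / 225 = 3.25 per year | 1 flare, 365.25 × 1 / 225 = 1.62 per year |
| 15 days | 2 flares | 2 flares |

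**3. How often the gap is exactly 14 days.** Let the two visits fall a and b days off schedule, each uniform on −7 to +7 (an assumption), with the recheck exactly 14 days after the first visit. The gap is 28 + b − a − 14 = 14 + (b − a), so it equals 14 only when a = b: 15 of 15 × 15 = 225 combinations, or 6.7%. If every visit is on schedule the share is 100%.

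**4. Draw versus course.** The general rule is about the onset, which for definition (b) is a blood draw. The repeat rule is about a course. Under protocol 6.4 the sample goes to the central laboratory, unblinded staff review the count, and they then contact the investigator to start capsules. If the course starts one or more days after the draw, a draw gap of 14 days means a course gap of at least 15, which meets the strict bound. Meeting the general rule then always satisfies the repeat rule. Applied together they reduce to one condition, a draw at least 14 days after resolution, and the Weeks 4, 8, 12 pattern gives 2 flares.

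**5. Effect on the rate test.** Assume 40 per arm, equal follow-up, no withdrawals, and one flare each in 24 placebo and 9 mepolizumab subjects. The Wilcoxon test is unstratified with tie correction and no continuity correction: z = (W − 1620)/√V, where W is the placebo rank sum, 1620 = 40 × 81/2, and V = (40 × 40/12) × [81 − Σ(t³ − t)/(80 × 79)], t being the tie-group sizes.

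| Subjects moved from 1 to 2 flares | Tie groups (0, 1, 2 flares) | W | z | p |
|---|---|---|---|---|
| none | 47, 33, 0 | 1920 | 3.39 | 0.0007 |
| 6 placebo | 47, 27, 6 | 1947 | 3.61 | 0.0003 |
| 4 mepolizumab | 47, 29, 4 | 1872 | 2.80 | 0.005 |
| all 9 mepolizumab | 47, 24, 9 | 1812 | 2.11 | 0.035 |

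Moving 2 placebo subjects gives p = 0.0005. Even with every flaring mepolizumab subject moved and no placebo subject moved, p stays below 0.05.

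**6. A borderline case.** With 22 versus 14 flaring subjects, moving 0, 2 or 4 placebo subjects gives p = 0.074, 0.054 and 0.039. The primary endpoint depends only on 22 versus 14. For a single-stratum CMH test, expected = 40 × 36/80 = 18 and variance = 40 × 40 × 36 × 44/(80² × 79) = 5.01, so z = 4/√5.01 = 1.79 and p = 0.074. The primary fails, the hierarchy stops, and the rate is never formally tested.

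**The case for a change.** The strongest reply is that no text says which bound governs or whether a course is dated by its draw or its first capsule. Nor does the missing onset depend on an exact 14-day gap: it applies to every third or later course. SAP 7.4.4.1 also reports a separate median rate for definition (b) flares. A sentence or two would settle all this before the treatment codes arrive.

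As a description of the text, that stands. A borderline rate result with a significant primary could also be constructed by moving mepolizumab subjects, so the checks above do not show that no dataset could be affected.

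The practical consequence does not stand. Each qualifying later course is declared an additional flare, and the second course is dated by the draw that triggered it. Dating the third in the same way is the obvious extension and the one that reproduces the plan's illustration. The illustration is not unconditional either: it sits in brackets inside the sentence that imposes the separation condition. Back-to-back courses with no below-threshold draw between them have no resolution date, so both bounds leave them as one flare. A count of courses minus one arises only if the brackets are detached from their sentence.

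Late, data-driven choice is also limited. The reading in step 4 comes from the text alone, and the planned listings of blinded OCS therapy and blood eosinophils (SAP 16.10.16, listings 17 and 53) let a reader check the count.

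**Conclusion.** No change is needed. The 14-day mismatch is a clerical slip, and the missing onset is a gap that an analyst fills in only one sensible way. The bounds part company only if a subject has at least three active courses, a below-threshold recheck, a new trigger at the next visit, a gap of exactly 14 days, and a course dated by its draw. Protocol 9.2.3 expects few definition (b) flares at all. For a subject who meets every condition, the rate is 1.62 or 3.25 per year, and the Week 20 to 32 status may turn on the same choice. The primary endpoint and time to first flare depend on the first flare only and cannot change.

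This rests on the uniform visit window for the 6.7% figure, on a lag of at least one day between draw and course for the joint reading, and on assumed flare counts with an unstratified test for the p-values. Writing one inequality in both sentences would be harmless tidying, with no shown gain in validity or interpretation.

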### **7.4.2. Summary Measure**

The difference between mepolizumab and placebo in the rate/year of HES flares.

### **7.4.3. Strategy for Intercurrent (Post-Randomization) Events**

The treatment effect to be estimated (estimand) will be the ‘treatment policy’ effect of initial randomised treatment. A treatment policy strategy will be used for the intercurrent events of a) discontinuation of study medication and b) receipt of alternative HES medications. For subjects withdrawing prematurely from the study during the 32-week treatment period, all data up to the time of study withdrawal will be used to calculate the rate of HES flares. Sensitivity analyses will be performed to examine the potential impact of the missing data.

### **7.4.4. Statistical Analyses / Methods**

Details of the planned displays are provided in [Appendix 10](#): List of Data Displays and will be based on GSK data standards and statistical principles.

